### **9.3.3 Removal of Subjects from Therapy or Assessment**

All subjects are free to withdraw from study participation at any time, for any reason, and without prejudice to their further medical care. In addition, the Investigator may terminate a subject from the study at any time. The primary reason for discontinuation from the study and/or study drug should be recorded on the eCRF using one of the following categories:

- Adverse Event. The subject experiences an AE that imposes an unacceptable risk to the subject's health, or the subject is unwilling to continue because of an AE. AEs requiring permanent study drug discontinuation per the protocol include:
  - A drug-related anaphylactic reaction.
  - A persistently severe drug-related AE that does not abate to mild or moderate intensity at least 2 weeks prior to the next scheduled dose.
  - Severe drug-related hyperglycemia (e.g., blood glucose > 250 mg/dL) that does not abate to mild or moderate intensity with anti-diabetic treatment (dose may be skipped up to 2 times prior to permanently discontinuing study drug; see [Section 9.4.6.3.2](#) for details).
  - Diagnosed or suspected IBD (e.g., diarrhea with or without blood or rectal bleeding associated with abdominal pain or cramping/colic, urgency, tenesmus, or incontinence for more than 4 weeks without a confirmed alternative diagnosis OR

endoscopic or radiologic evidence of enteritis/colitis without a confirmed alternative diagnosis).

- Lack of Efficacy. Removal of a subject from the study is at the discretion of the Investigator and may occur if the Investigator determines that study drug administration is not benefitting the subject and eye symptoms linked to progressing disease worsen posing an unacceptable risk to the subject. The specific care of the subject is best determined by the Investigator and managing physician(s) involved in the subject's care and may require removal from the study. All subjects are free to withdraw from study participation at any time, for any reason, allowing them to receive any specific treatment for TED that is considered necessary per their treating physician and local standard of care.
- Non-Compliance with Study Drug/Other/Protocol Deviations. The subject has a significant protocol deviation, does not comply with study drug administration schedule, or fails to adhere to other study requirements as stated in the protocol.

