6.3.5. Efficacy Assessments

For the binary primary and secondary endpoints, subjects missing the evaluations at a given visit will be treated as failures (non-responders). No imputation of missing data will be performed for any continuous efficacy assessments.

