8.1. PRIMARY EFFICACY ENDPOINT AND ANALYSIS

The primary efficacy endpoint is the proptosis responder rate (percentage of subjects with a ≥ 2 mm reduction from Study Baseline in proptosis in the study eye, without deterioration [≥ 2 mm increase] of proptosis in the fellow eye) at Week 24 in the ITT Population.

Proptosis assessments will be performed using a Hertel exophthalmometer provided by the Sponsor for consistency in measurement, and (except when strictly unavoidable) the same Hertel instrument and same observer should be used at each evaluation for the full duration of the study. Additionally, the same intercanthal distance (ICD) must be used on each occasion.

Proptosis will be measured for each eye at Day 1 and Weeks 6, 12, 18, and 24 (or PW) during the Treatment Period, and for HZNP-TEP-301 proptosis non-responders at Weeks 28, 36, 48 (or PW) during the Follow-Up Period. Measurements will be recorded on the Clinical Measures of Severity eCRF under exophthalmos.

Subjects missing the Week 24 evaluation will be considered to be treatment failures (non-responders) for the primary analysis. Further, subjects who prematurely discontinue study drug dosing prior to Week 21 during the Treatment Period will be analyzed as treatment failures (non-responders), unless an assessment at Week 24 (within the day range specified in Section 6.4) is available.

Descriptive summaries of responder results of study eye will be provided by treatment received in HZNP-TEP-301 and overall at Week 24.

In addition, descriptive summaries of responder results will be provided by treatment received in HZNP-TEP-301 for each visit in the Treatment Period and for HZNP-TEP-301 proptosis non-responders in the Follow-Up Period for the ITT Population, considering subjects missing the evaluations as treatment failures (non-responders). Similar summaries will also be provided separately for the fellow eye, and by subject enrollment type (subjects who were proptosis non-responders in HZNP-TEP-301, subjects who relapsed during the Follow-Up Period in HZNP-TEP-301), tobacco use status (non-user, user), region (US, EU), site, age group (<65 years, ≥ 65 years), gender, race (white, black or African American, Asian, other), and ethnicity (Hispanic or Latino, not Hispanic or Latino). A plot of proportion of proptosis responder by visits and treatment received in HZNP-TEP-301 will also be provided.

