In addition, a separate analysis will be provided for time to proptosis response. Time to proptosis response will be measured as the days from the first dose date to the earliest visit date in which the criteria are met for proptosis response (≥ 2 mm reduction from Study Baseline in proptosis in the study eye, without deterioration [≥ 2 mm increase] of proptosis in the fellow eye) within the Treatment Period, calculated as:

first visit date in which criteria for proptosis response are met - first dose date + 1

Subjects not achieving a proptosis response within the Treatment Period will be censored at their last visit date with a proptosis assessment within the Treatment Period. Kaplan-Meier estimates will be provided by treatment received in HZNP-TEP-301 of the 25th percentile, median, and 75th percentile. 95% confidence intervals (CI) will be provided for the median. Analyses will be based on the ITT Population. Any ITT subject who is enrolled but not dosed will be censored at Day 0.

The analysis will be repeated for the fellow eye (using a definition analogous to the one used for the study eye).

Plots of the time to proptosis response will be provided by treatment received in HZNP-TEP-301 for the study eye and fellow eye.

Further, for subjects who were proptosis non-responders in HZNP-TEP-301, sustained proptosis response at a given visit in the HZNP-TEP-302 Follow-Up Period will be defined for HZNP-TEP-302 Week 24 proptosis responders as:

- ≥ 2 mm reduction from Baseline in proptosis in the study eye, without deterioration (≥ 2 mm increase) of proptosis in the fellow eye, AND
- No additional TED treatment received by the time of the visit.

Additional TED treatment will include any instances of TED medication (identified by manual listing review), TED concomitant procedures (identified by manual listing review), TED surgical procedures, and/or orbital radiation treatments.

At each assessment after Week 24, the proportion of subjects who are sustained responders will be summarized by treatment received in HZNP-TEP-301. Subjects who are missing proptosis values at a visit will be considered non-responders at that visit.

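### Time to proptosis response censors subjects who stop early without a response, so the Kaplan-Meier curve can only match or exceed one that counts them as non-responders (minor, cheap to fix)

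*SAP*

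**What the plan says.** The event in SAP 8.1 is first response, dated at "the earliest visit date in which the criteria are met for proptosis response" within the Treatment Period. A response later lost still counts. For everyone else the rule is "Subjects not achieving a proptosis response within the Treatment Period will be censored at their last visit date with a proptosis assessment", which covers subjects who complete Week 24 and subjects who stop early alike. For the undosed: "Any ITT subject who is enrolled but not dosed will be censored at Day 0".

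The output is: "Kaplan-Meier estimates will be provided by treatment received in HZNP-TEP-301 of the 25th percentile, median, and 75th percentile". A 95% confidence interval for the median and plots are also planned, and the analysis is repeated for the fellow eye.

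The primary analysis in the same section works differently: "Subjects missing the Week 24 evaluation will be considered to be treatment failures (non-responders) for the primary analysis". Subjects who stop dosing before Week 21 are also failures, unless a Week 24 assessment inside the SAP 6.4 day range exists. The by-visit responder summaries likewise score a missing evaluation as failure. SAP 6.3.5 confines failure imputation to binary endpoints, so it does not reach time to response.

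Protocol 9.3.3 lists lack of efficacy among the reasons for discontinuation. Removal on that ground "may occur if the Investigator determines that study drug administration is not benefitting the subject" and eye symptoms of progressing disease worsen to an unacceptable risk. It adds that subjects may withdraw at any time, which leaves them free to receive other TED treatment.

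**The concern.** Kaplan-Meier assumes that a censored subject would go on to respond at the same rate as those still followed. A subject who stops for want of benefit is a poor fit to that assumption. Such a subject is due a premature-withdrawal visit that includes proptosis. If there is no response there, an observed lack of response is entered as unknown from that date on.

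One SAP section would therefore yield a responder-by-visit plot that counts these subjects as failures and a Kaplan-Meier plot that removes them from the denominator. The SAP offers no justification for non-informative censoring and no sensitivity analysis for this curve. In an open-label study without a control group, response-time quartiles may be read as efficacy evidence, and any departure runs only in the favourable direction.

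**Working it through.** **Inputs from the documents.** Post-baseline proptosis visits are at Weeks 6, 12, 18 and 24 (SAP 8.1), with target Days 43, 85, 127 and 169 (SAP 6.4). The Week 24 visit window is ±7 days, so it closes on Day 169 + 7 = 176, which is also the upper limit for Week 24 in Table 2 of SAP 6.4. The plan gives no expected response time, sample size or dropout rate, so there is no figure to reproduce. Every N, response pattern and number of leavers below is an assumption.

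**Direction.** Let N be the ITT number, d_k the first responses at visit k, D_(k-1) the responses before visit k, and r_k the number still at risk under the SAP rule.

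- SAP rule: S(t) = product of (1 - d_k / r_k).
- Leavers kept as non-responders: S*(t) = product of (1 - d_k / (N - D_(k-1))) = 1 - D_k / N.

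Censoring removes subjects from r_k, so r_k ≤ N - D_(k-1) at every visit and S ≤ S*. The response curve 1 - S is never lower and its percentiles are never later. A check on 20,000 random event and censoring patterns found no exception. With no early stoppers or undosed subjects, and all visits on their target days, the two curves coincide.

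**Example A (assumed): N = 40, 12 respond at Week 6, then 4 non-responders leave.** Later responses are 10 of 24, 5 of 14 and 2 of 9.

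| Day | SAP censoring | Leavers as non-responders |
|---|---|---|
| 43 | 12/40 = 30.0% | 30.0% |
| 85 | 1 - 0.70(14/24) = 59.2% | 22/40 = 55.0% |
| 127 | 1 - 0.70(14/24)(9/14) = 73.8% | 27/40 = 67.5% |
| 169 | 1 - 0.70(14/24)(9/14)(7/9) = 79.6% | 29/40 = 72.5% |

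The 25th percentile is Day 43 and the median Day 85 under both rules. The 75th is Day 169 under the SAP rule and not reached otherwise.

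**Example B (assumed): as A, but 8 leave; later responses 8 of 20, 4 of 12, 2 of 8.** At Day 169 the SAP rule gives 1 - 0.70(12/20)(8/12)(6/8) = 79.0%, against 26/40 = 65.0%. The 25th percentile is again unchanged. The failure-counted curve is exactly 20/40 = 50% at Day 85, so the median is at the boundary. The 75th percentile is Day 169 against not reached.

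**Example C (assumed): N = 20, first responses 4, 3, 2, 1.**

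- One leaver before each visit: 1 - (15/19)(11/14)(8/10)(6/7) = 57.5%, against 10/20 = 50.0%. The median is Day 127 against Day 169.
- Two leavers only (one before Day 43, one between Days 43 and 85): 1 - (15/19)(11/14)(9/11)(8/9) = 54.9%, against 50.0%. No quartile moves.

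**Leavers spread evenly over the four intervals (assumed first-response curve 30/50/60/70%).** Kaplan-Meier stays at 70.0% at Week 24. Keeping leavers as non-responders gives 67.6%, 65.2% and 60.4% at 5%, 10% and 20% dropout. The median goes from Day 85 to Day 127, but this curve was set to reach exactly 50% at Day 85, so any dropout would shift it.

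**Completers.** Because actual visit dates are used, the Week 24 window adds a second, smaller effect. Assume 40 completers, of whom 20 respond before Week 24. At Week 24, 5 respond and 5 do not on Day 165, and the same happens on Day 172. Kaplan-Meier gives 1 - 0.5(15/20)(5/10) = 81.3%, against 30/40 = 75.0%, with no dropout at all. Moving only the early stoppers to a later censoring date would leave this in place.

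**The case against.** Time to response is not a listed endpoint in SAP 4 or Protocol 9.6.1. It is descriptive and carries no test. The SAP already plans failure-imputed responder summaries at the same four visits, with a plot. Removal for lack of efficacy is narrowly worded, and leavers may instead go for adverse events, non-compliance, loss to follow-up, voluntary withdrawal or pregnancy. For those subjects, never responding is a conservative bound and not an unbiased estimate. A premature-withdrawal visit can also still capture a response. SAP 12 expects the ITT and Safety populations to be identical, so undosed subjects should be few or none.

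All of this stands and limits the point to a minor one. It does not remove it. The by-visit summaries show response at each visit, not cumulative first response, so they do not replace the curve. A listed route out of the study that depends on outcome is enough to put non-informative censoring in doubt, and the SAP does not address it.

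**Conclusion.** The point holds as a minor one. The direction is certain; the size cannot be derived from the documents. In the assumed examples with leavers, the Week 24 Kaplan-Meier proportion is higher by 2.4 to 14 percentage points. With few leavers, spread over only four visits, the quartiles may not change. The effect on the confidence interval of the median was not calculated.

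A reader might infer more, in three ways that the documents do not support:

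- *That all three quartiles are distorted.* In Example A only the 75th percentile moves, and with two leavers in Example C none does.
- *That the censoring explains any gap from the primary result, or that the primary result is affected.* The primary endpoint is response at Week 24 and has its own failure rule. The curve counts first response ever, including responses later lost and responders who then stop and fail the primary. The two can differ even after the fix.
- *That every early stopper is a primary-analysis failure.* A subject who stops dosing but has an in-window Week 24 assessment is analysed on that assessment.

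**What to change.** In the time-to-response text of SAP 8.1, for both the study-eye and fellow-eye analyses:

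- Count as an event, at its actual date, any first response in the Treatment Period, including one at a premature-withdrawal visit or at an in-window Week 24 assessment after dosing has stopped.
- Censor every other ITT subject at one common time: early stoppers, undosed subjects and Week 24 completers alike. Use Day 176, or the latest actual Week 24 visit if any falls later. A response dated after the common day would otherwise be divided by a depleted risk set.
- State that the curve is then the ITT cumulative proportion with a first response (1 - S* above).
- Keep the present censoring rule as a sensitivity analysis.

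The cost is about one sentence, one date derivation and a repeat run under the present rule. The percentiles will be somewhat less favourable, and the assumption is conservative for subjects who leave for reasons unrelated to efficacy. The sensitivity analysis shows how much that matters.

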8.2. SECONDARY EFFICACY ENDPOINTS AND ANALYSES

8.2.1. CAS Categorical Response

The CAS will be completed at Day 1 and Weeks 6, 12, 18, and 24 (or PW) during the Treatment Period, and for HZNP-TEP-301 non-responders at Weeks 28, 36, 48 (or PW) in the Follow-Up Period using the 7 item European Group on Graves' Ophthalmopathy (EUGOGO) amended CAS (Mourits et al, 1989) for each eye.

For each item present, one point is given. The sum of these points is the total score.

- Spontaneous orbital pain
- Gaze evoked orbital pain
- Eyelid swelling that is considered to be due to active (inflammatory phase) TED/GO
- Eyelid erythema
- Conjunctival redness that is considered to be due to active (inflammatory phase) TED/GO (ignore "equivocal" redness)
- Chemosis
- Inflammation of caruncle or plica

The first secondary endpoint is CAS as a categorical response variable defined as a reduction to a CAS of 0 or 1 from Study Baseline at Week 24. Subjects missing the Week 24 evaluation will be considered to be treatment failures (non-responders) for the analysis. Descriptive summaries of responder results will be provided for the study eye and fellow eye by treatment received in HZNP-TEP-301 for the ITT Population at Week 24. Only subjects with CAS > 1 at study baseline in the ITT Population will be summarized.

In addition, descriptive summaries of responder results will be provided for the study eye and fellow eye by treatment received in HZNP-TEP-301 for the ITT Population for each visit in the Treatment Period and for HZNP-TEP-301 proptosis non-responders in the Follow-Up Period, considering subjects missing the evaluations as treatment failures (non-responders). Similar summaries will also be provided separately by subject enrollment type (subjects who were proptosis non-responders in HZNP-TEP-301, subjects who relapsed during the Follow-Up Period in HZNP-TEP-301), tobacco use status (non-user, user), region (US, EU), and site. The proportion of subjects with a complete CAS response (subjects who have a CAS of 0) in the study eye will be summarized for each visit in the Treatment Period and Follow-Up Period considering observed results only. Only subjects with CAS > 0 at study baseline in the ITT Population will be summarized.

Summaries after Week 24 for subjects who were proptosis non-responders in HZNP-TEP-301, will also include a summary of sustained CAS response, where sustained responder

is defined for subjects who were a responder at Week 24 and remained a responder post-Week 24 (defined as having a reduction to a CAS of 0 or 1 in study eye) and did not receive any additional TED treatment by the time of the visit. Additional TED treatment will include any instances of TED medication (identified by manual listing review), TED concomitant procedure (identified by manual listing review), TED surgical procedures, and/or orbital radiation treatments. At each assessment after Week 24, the proportion of subjects who are sustained responders will be summarized by treatment received in HZNP-TEP-301. Subjects who are missing values at a visit will be considered non-responders at that visit.

A plot of proportion of CAS categorical responder by visits and treatment received in HZNP-TEP-301 will also be provided.

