### **9.6.1 Endpoints**

Study endpoints will be evaluated for all subjects from Baseline to Week 24.

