#### **9.6.1.2 Secondary Endpoints**

1. Percentage of subjects with a CAS value of 0 or 1 in the study eye at Week 24.
2. Mean change from Baseline to Week 24 in proptosis measurement in the study eye.
3. Diplopia responder rate (percentage of subjects with baseline diplopia  $> 0$  in study eye who have a reduction of  $\geq 1$  grade with no corresponding deterioration [ $\geq 1$  grade worsening] in the fellow eye) at Week 24.
4. Mean change from Baseline to Week 24 in the GO-QoL questionnaire overall score.

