3.2. SECONDARY OBJECTIVES

Secondary objectives are:

1. Percentage of subjects with a Clinical Activity Score (CAS) value of 0 or 1 at Week 24 in the study eye.
2. Mean change from Study Baseline to Week 24 in proptosis measurement in the study eye.
3. Diplopia responder rate (i.e. the percentage of subjects with Study Baseline diplopia > 0 in study eye who have a reduction of ≥ 1 grade with no corresponding deterioration [≥ 1 grade worsening] in the fellow eye) at Week 24.
4. Mean change from Study Baseline to Week 24 in the Graves' Ophthalmopathy Quality of Life (GO-QoL) questionnaire overall score.

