4.2. SECONDARY EFFICACY ENDPOINTS

The secondary endpoints are the following:

1. Percentage of subjects with a CAS value of 0 or 1 in the study eye at Week 24.
2. Mean change from Study Baseline to Week 24 in proptosis measurement in the study eye.
3. Diplopia responder rate (percentage of subjects with Study Baseline diplopia >0 in study eye who have a reduction from Study Baseline of ≥ 1 grade with no corresponding deterioration [≥ 1 grade worsening] in the fellow eye) at Week 24.
4. Mean change from Study Baseline to Week 24 in the GO-QoL questionnaire overall score.

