5. ANALYSIS POPULATIONS

5.1. INTENT-TO-TREAT POPULATION

The Intent-to-Treat (ITT) Population will include all subjects who are enrolled (signed informed consent) in the study. Subjects will be analyzed according to treatment received in HZNP-TEP-301 study. The ITT Population will be used for all analyses of efficacy and safety endpoints.

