8. EFFICACY

Efficacy assessments will be performed for both eyes at each assessment time point; however, only the study eye will be used to assess the primary efficacy endpoint. All summaries of efficacy endpoints will be conducted based on ITT population.

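### SAP Section 8 puts baseline conditions on the CAS 0/1 and overall-response rates that Section 4 does not state, and counts a held best grade as response; Section 12 lists none of this

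*SAP*

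**What the plan says.** Protocol 9.6.1.2 gives the first secondary endpoint as "Percentage of subjects with a CAS value of 0 or 1 in the study eye at Week 24". SAP 3.2 has the same content: "Percentage of subjects with a Clinical Activity Score (CAS) value of 0 or 1 at Week 24 in the study eye". SAP 4.2 repeats it. None of the three mentions baseline CAS. The diplopia endpoint in the same SAP list does carry a baseline condition: "percentage of subjects with Study Baseline diplopia >0 in study eye".

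SAP 8.2.1 describes the CAS endpoint differently, as a response "defined as a reduction to a CAS of 0 or 1 from Study Baseline at Week 24". The Week 24 paragraph then closes with "Only subjects with CAS > 1 at study baseline in the ITT Population will be summarized". Both eyes are summarised, but the sentence does not say which eye must meet the condition. The by-visit paragraph that follows does not repeat the limit. Its only baseline limit, CAS above 0, is attached to the complete-response summary.

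SAP 8.3.1 has the same structure. Overall response at Week 24 is limited to subjects with baseline CAS > 1 and proptosis > 1 mm; the by-visit paragraph states no such limit. SAP 4.3 and protocol 9.6.1.3 define this rate without either condition.

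SAP 8.3.2.1 and protocol Table 9.3 give a minimum change for each severity item. Below its table the SAP adds that a subject already at the best possible assessment counts as a responder if that assessment is held.

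SAP Section 12 reports four departures: ITT replacing the Safety Population, an added PK Population, added analyses from the HZN-001 Baseline, and one subject's COVID-delayed data. None of the rules above is there.

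**The concern.** A named secondary endpoint has two definitions inside one SAP. Section 4 describes a level at Week 24 in all subjects; Section 8.2.1 describes a fall to that level among those who started above it. These are different quantities with different denominators. A programmer working from the by-visit paragraph could defensibly produce either.

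The overall-response limit removes only subjects who cannot achieve a 2-point CAS fall or a 2 mm proptosis fall, so it raises the percentage without any change in the number of responders. The maintenance rule puts improvement and stability into one percentage, and a reader cannot separate them. In both cases the reported rate would not be the one that the endpoint list leads the reader to expect, and the section meant to announce such changes does not mention them.

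**Working it through.** The plan gives no figure to reproduce: it has no sample-size calculation and no baseline CAS distribution. All shares below are assumptions, except 29/42, which is the teprotumumab overall-response result of the earlier TED study in protocol 7.1.3.4.2.

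**Step 1. Definition against rule.**

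| Endpoint | Protocol / SAP Section 4 | SAP Section 8, Week 24 | SAP Section 8, by visit | SAP Section 12 |
|---|---|---|---|---|
| CAS 0/1 (secondary) | no baseline condition | fall to 0 or 1; baseline CAS > 1; eye not named | limit not repeated | not listed |
| Overall response (exploratory) | no baseline condition | baseline CAS > 1 and proptosis > 1 mm | limit not repeated | not listed |
| Severity items (exploratory) | minimum change (protocol Table 9.3) | minimum change, or best grade held | same classification | not listed |

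**Step 2. Can anyone start at CAS 0 or 1?** Protocol 9.3.1 admits lead-in non-responders on proptosis alone. Under 9.3.4 relapse can be met by a proptosis increase, with symptoms also considered. Neither sets a CAS floor. Section 9.3.2 also applies the lead-in study's exclusion criteria, which are not shown. So low baseline CAS is possible, and its frequency is unknown.

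**Step 3. Overall response.** Let a be the share of subjects dropped (read here as study-eye CAS 0-1) and q the rate in the subset. Dropped subjects cannot respond, so the all-ITT rate is (1 - a) x q, and the subset rate is 1/(1 - a) times as large. Taking q = 29/42 = 69% purely as an illustration:

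| a | factor 1/(1 - a) | subset rate | all-ITT rate |
|---|---|---|---|
| 5% | 1.05 | 69% | 66% |
| 10% | 1.11 | 69% | 62% |
| 20% | 1.25 | 69% | 55% |
| 30% | 1.43 | 69% | 48% |

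**Step 4. CAS 0/1.** Let m be the share of low-CAS starters who are at 0 or 1 at Week 24, and r the share of the others who get there (missing counts as failure in both). Section 4 rate = a x m + (1 - a) x r. Section 8.2.1 rate = r. The difference, 8.2.1 minus Section 4, is -a(m - r).

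- m = 90%, r = 60%, with a = 5, 10, 20, 30%: -1.5, -3, -6, -9 points.
- m = r: 0.
- m = 50%, r = 60%, same values of a: +0.5, +1, +2, +3 points.
- Wider grid, a from 10 to 40%, r 40 or 60%, m from 50 to 90%: from -20 to +4 points.

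The sign depends on m against r, and neither is known.

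**Step 5. Severity items.** Let b be the share at the best grade at baseline, h the share of these who hold it, and i the share of the rest who improve by the minimum change. SAP rate = b x h + (1 - b) x i. Minimum change on all ITT = (1 - b) x i. Among those able to improve, the rate is i. With h = 90% and i = 40%:

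| b | SAP 8.3.2.1 | minimum change, all ITT | minimum change, able to improve |
|---|---|---|---|
| 10% | 45% | 36% | 40% |
| 30% | 55% | 28% | 40% |
| 50% | 65% | 20% | 40% |

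The excess over the all-ITT change rate is b x h, which cannot be negative.

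**The case against.** The strongest reply is that protocol 9.6 lets the SAP supersede the protocol, and that the rules are written openly in the SAP body. That settles SAP against protocol. It does not settle SAP Section 4 against SAP Section 8.

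A second reply is that little is lost. SAP 14.2.5.2 requires denominators in footnotes, column headings carry the ITT N, and Listing 16.2.6.2.2 gives CAS for all subjects. This stands in large part. The all-ITT overall-response rate is the responder count divided by N. The Section 4 CAS 0/1 rate cannot be rebuilt from a subset table, but it can be from the listing. The data stay available; a secondary endpoint should still not have to be rebuilt by hand.

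Third, each rule has a rationale. Excluding subjects already at target is a reasonable way to measure improvement, and where m exceeds r it gives the lower CAS 0/1 rate. The protocol is silent on subjects who cannot improve on a severity item. The four-category analysis in 8.3.4 classifies every subject, but its low-responder class can be reached from a baseline CAS of 1, so a wider denominator there makes sense. Diplopia in 8.2.3 and the diplopia severity item are separate endpoints and may follow different rules. All of this stands. It argues for keeping the subset analysis and the maintained category visible, not for leaving the definitions unreconciled.

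A reader might also argue that subsetting is barred outright, because protocol 9.6.1 says "Study endpoints will be evaluated for all subjects from Baseline to Week 24" and the SAP says "The ITT Population will be used for all analyses of efficacy and safety endpoints" and "All summaries of efficacy endpoints will be conducted based on ITT population". The documents do not support that. The diplopia endpoint is itself a subset, and its tables are labelled ITT. The argument rests on the endpoint definitions, not on these general statements.

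**Conclusion.** The inconsistency is real and should be corrected. Its size is unknown, because the documents give neither the share starting at CAS 0 or 1 nor the share at the best grade of each item; the first could be small. The direction is known for two exploratory results. The overall-response limit can only raise the rate, by 1/(1 - a), and the maintenance rule can only raise a severity-item rate above the minimum-change rate on all ITT. Step 3 reads the CAS condition as applying to the study eye, and its 69% comes from a recent-onset population, so it shows scale only.

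Two stronger readings go too far. One is that the CAS 0/1 rate will never be reported as Section 4 defines it. That is likely at Week 24 but not certain: the by-visit paragraph orders ITT summaries that include Week 24 and carries no CAS > 1 limit, while the index plans a single by-visit table against Study Baseline, and the mock-ups are in a separate file. The text is ambiguous, not settled. The other is that Section 8 inflates the secondary endpoint. Step 4 shows that the CAS 0/1 rate can move either way.

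The primary endpoint is untouched, and all analyses are descriptive, so no error rate or power is involved.

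**What to change.** 1. Report CAS 0/1 and overall response at Week 24 and by visit on all ITT subjects, as SAP Section 4 defines them, beside the baseline CAS > 1 subset (with proptosis > 1 mm for overall response). Show both denominators and name the eye to which the CAS > 1 condition applies. SAP 8.2.3 is a model: it names the eye and gives the condition for each baseline.
2. For each severity item, show subjects improved by the Table 9.3 minimum change and subjects who maintained the best grade in separate rows, with the number able to improve.
3. Align SAP Sections 4 and 8, state whether the limits apply to the by-visit tables, and list these rules in Section 12.

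The cost is SAP wording, one extra denominator per table and one extra row per severity item. No new data are needed. The overall-response and improvement rates will look lower than under the present rules. Which CAS 0/1 rate leads, and whether the maintained category keeps a responder label, is partly preference once both are shown.
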